### 6.3.2 Day 7 and Day 14 Visit

All participants will return to the clinic on Day 7 and 14. Prior to the administration of the study drug (if applicable), the participant will be evaluated clinically to assess for the development of clinically significant conditions that may contraindicate dosing.

- Vital signs (including sitting heart rate and blood pressure)
- Blood samples for central lab hematology, chemistries and iron indices (Group A participants will have an additional blood sample for PK prior to dosing).
- Concomitant medications assessment
- Adverse events assessment
- ESA and IBD stability (if applicable)

For Group A participants the following will be performed on **Day 7 only**:

- Blood samples for PK immediately (within 5 minutes) post-dose and 60 minutes post dose.
- Verify amount of single FCM dose (15mg/kg up to a maximum dose of 750 mg).
- Pre-administration evaluation to include measurement of heart rate, blood pressure, and body temperature.
- Administer FCM as a slow IV injection at the rate of approximately 2 mL /minute or in no more than 250 mL of normal saline and infused over 15 minutes.
- Document start and stop time of FCM administration and the total dose administered and if diluted.
- Post-administration, obtain sitting heart rate and blood pressure immediately (within 5 minutes) after and 30 minutes after FCM administration.

For Group B participants the following will be performed:

- Oral iron dispensing (**Day 7 and Day 14**).
- Compliance will be assessed according to the following:

For ferrous sulfate tablets:

- Used blister packs will be returned and are to include both the empty containers and any unused medication.
- The blister packs will be examined to assess compliance (the number taken divided by the number of pills expected to be taken). A record of compliance will be maintained for each participant and reviewed.
- If the participant took less than the number of tablets expected, document the reason(s) for missed doses and counsel the participant/parent/guardian about the importance of taking the study drug as prescribed.

For ferrous sulfate drops and elixir:

- Used oral syringes will be returned which will include any unused medication.

- The oral syringes will be examined to assess compliance (the volume remaining in the oral syringes divided by the expected amount to be taken). A record of compliance will be maintained for each participant and reviewed.
- If the participant took less than the volume expected, document the reason(s) for missed doses and counsel the participant/parent/guardian about the importance of taking the study drug as prescribed.

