### 3.4 Schedule of Events

Visit Day	Screening (Day -7 + 1)	Day 0	Day 7	Day 14	Day 28	Day 35
Informed Consent / Assent	X					
Medical History	X					
Physical Exam		X				X
Inclusion/Exclusion Criteria	X	X				
IRT	X	X				X
Vital Signs	X	X	X	X	X	X
Weight	X	X				
Height	X					
Temperature		X	X			
Hematology, Chemistry and Iron Indices 	X	X	X	X	X	X
Serum Pregnancy Test	X					X
Concomitant Medications	X	X	X	X	X	X
IBD Treatment / ESA Stability (if applicable)	X	X	X	X	X	X
Adverse Event Assessments		X	X	X	X	X
Randomization		X				
Injectafer ® Dosing		X	X			
Pharmacokinetic Sampling 		X	X			
Oral Iron Dosing		X	X	X	X	
Oral Iron Dispensing		X	X	X		
Oral Iron Compliance Assessment			X	X	X	

For a full description of central laboratory assessments, refer to Protocol Section 6.4.

Blood samples for pharmacokinetic analysis will be collected pre-dose, immediately (within 5 minutes) post-dose, and 60 minutes post-dose for participants receiving FCM. For a full description of the pharmacokinetic parameters, refer to Protocol section 6.3.6.

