### 4.2 Screening Phase

A subject who enters the screening phase will be assigned, via the IRT system, a unique screening number. From the time of consent until the start of treatment with study drug, the participant will not receive any form of supplemental iron outside of the study (intravenous or blood transfusion iron from 4 weeks prior to consent or oral iron including multivitamins with iron from time of consent). Dietary iron intake will not be restricted during participation in the study.

If the participant does not qualify for study entry, the participant should be entered into the IRT system as a screen failure. Participants can be re-screened once (**See section 6.2**).

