### **6.3.3 Day 28**

- Vitals signs
- Hematology, chemistries and iron indices
- Concomitant medications assessment
- ESA and IBD stability (if applicable)
- Adverse events assessment
- For Group B participants, oral iron compliance assessment

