### **6.3.6 Pharmacokinetic Sampling**

Blood samples will be collected for PK assessment pre-dose, immediately (within 5 minutes) post-dose, and 60 minutes post-dose for participants receiving FCM on Days 0 and 7. Blood samples should be taken at approximately the same time of day (within 1 hour) on Day 7 as Day 0.

The pharmacokinetic parameters to be analyzed in this study are as follows: the maximum serum concentration ( $C_{max}$ ) and the time at which  $C_{max}$  occurs ( $T_{max}$ ), the area under the

serum concentration-time curve from time zero to the last sampling time with a quantifiable concentration ( $AUC_{0-\text{time last measured concentration}}$ ), the extrapolated area under the serum concentration-time curve from time zero to infinity ( $AUC_{0-\text{infinity}}$ ), and the half-life ( $T_{1/2}$ ). The secondary parameters were the mean residence time (MRT), the apparent serum clearance (Cl), and the apparent volume of distribution ( $V_D$ ), which includes the initial volume of distribution following the injection ( $V_{Dc}$ ), the volume of distribution at the steady state ( $V_{Dss}$ ), and the volume of distribution at the final elimination ( $V_{Darea}$ ).

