### 2.3.4 Handling of Missing Data

A participant who withdraws from the study for any reason will be included in the analyses regardless of time on study. Methods for handling withdrawals and missing data will be specific to each endpoint to be analyzed. Missing data will not be imputed for descriptive statistical summaries in safety or efficacy.

For statistical inferential (models) analyses, missing data will be imputed using last observation carried forward (LOCF) method for hemoglobin and other efficacy endpoints. e.g. for primary endpoint, hemoglobin, when Day 35 data is missing (subject has discontinued before Day 35, or measurement not taken at Day 35 though subject was not discontinued), Day 28 result will be carried forward. If the post-baseline value of the first scheduled visit is missing, the worst value obtained from the same time point of all subjects in ITT population will be used for both treatment groups. The worst value is defined as the lowest value for hemoglobin, ferritin, TSAT and reticulocyte hemoglobin content.

Supportive analyses will assess the impact of missing values on inferences based on primary efficacy endpoints and missing data will be handled by using missing at random (MAR) in

mixed effect model repeat measurement (MMRM) model. The observed case will also be applied for primary analysis.

Dates missing the day or both day and month of the year will adhere to the following conventions to classify TEAE and to classify prior/concomitant medications.

- A medication with a completely missing start date will be considered a prior medication. A medication with a completely missing stop date will be considered a concomitant medication.
- If complete AE onset date is missing and AE end date is on or after the first dose date then it will be counted as a treatment emergent AE (TEAE) for the study. If complete AE onset date is missing and AE end date is before the first dose date then it will be counted as a not treatment emergent AE (TEAE) for the study.
- If an AE or a medication has a partial missing start or stop date, the following rules will be used for imputation:
  - If year is present but month and day are missing, impute start date as January 1 of that year or first dose date if the year is the same as the year of first dose date and impute stop date as December 31 of that year.

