### **6.2.2 Change in TSAT from baseline to Day 35**

The actual value of TSAT on baseline, Day 35, and change from baseline to Day 35 will be summarized via descriptive statistics by treatment group.

Treatment group difference for change in TSAT will be assessed with the analysis of covariance (ANCOVA), with treatment and randomization strata (hemoglobin and age categories) as fixed factors and baseline value of TSAT as a covariate. Missing value will be imputed using LOCF as specified in [Section 2.3.4](#). P-values to test treatment effect will be determined. Point estimates, associated 95% confidence interval and p-values will be reported.

To assess the robustness of this secondary efficacy analysis, supportive analyses will be performed using the following approach:

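### Oral-arm TSAT at Days 7 and 14 (and Day 28, if a dosing day) has no fixed time from the oral dose, and LOCF carries earlier-phase values into the Day 35 TSAT and ferritin analyses when Day 35 is missing

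*Protocol*

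**What the plan says.** **Sampling in the oral arm.** For Days 7 and 14, Protocol 6.3.2 lists "Blood samples for central lab hematology, chemistries and iron indices (Group A participants will have an additional blood sample for PK prior to dosing"). The pre-dose condition belongs to the FCM group's PK sample. The only other ordering text there is "Prior to the administration of the study drug (if applicable), the participant will be evaluated clinically", which concerns a check for contraindications. Day 28 (6.3.3) lists "Hematology, chemistries and iron indices" with no timing. After the first in-clinic dose, a parent or guardian gives oral iron twice a day (6.3.1). The schedule row "Oral Iron Dosing" (3.4) is marked at Days 0, 7, 14 and 28, while 5.2 describes a 28-day course.

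**Where timing is controlled.** At Day 0, 6.3.1 puts the blood draw before study drug in both arms. For PK samples, taken only in the FCM arm, 6.3.6 adds: "Blood samples should be taken at approximately the same time of day (within 1 hour) on Day 7 as Day 0".

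**Screening and baseline.** Section 4.2 bars "oral iron including multivitamins with iron from time of consent". Consent is obtained at the screening visit, where the qualifying TSAT is also drawn. Protocol 6.3.1 lists Day 0 blood after treatment assignment, and SAP 2.3.1 takes the last pre-randomization value as baseline. On that order the screening TSAT is the baseline.

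**Analysis.** SAP 2.3.4 says that "missing data will be imputed using last observation carried forward (LOCF) method for hemoglobin and other efficacy endpoints", with Day 28 carried to Day 35 as its example. SAP 6.2.2 applies this to TSAT ("Missing value will be imputed using LOCF as specified in" Section 2.3.4), and 6.2.1 does the same for ferritin. The supportive MMRM imputes nothing but drops the treatment-by-visit term when it is not significant. An observed-case analysis is named only for the primary analysis.

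**The concern.** TSAT is serum iron as a share of iron-binding capacity. If serum iron rises for some hours after an oral dose, TSAT rises with it, whatever the child's iron stores. An oral-arm sample at Day 7 or 14 may fall just before a dose, shortly after it, or half a day later, and the data will not show which. This source of variation exists in one arm only.

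It reaches the results by three routes: the by-visit TSAT summaries; the MMRM treatment effect, if visits are pooled; and the Day 35 ANCOVA, when an on-drug value stands in for a missing Day 35 value. The third route has a counterpart that does not depend on dose timing. Day 35 lies about 7 days after oral iron ends and 28 days after the second FCM dose, so any carried ferritin or TSAT value, in either arm, describes a different treatment phase.

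Day 35 ferritin and TSAT are the first two named secondary endpoints. Each gets a p-value, with no multiplicity correction.

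**Working it through.** **The plan's own figure.** The only design calculation is for hemoglobin: difference 1.0 g/dL, SD 1.16, two-sided alpha 0.05, power 90%. n per arm = 2 × (1.960 + 1.282)² × 1.16² / 1.0² = 28.3, so 29; the t-based solution is 29.3, so 30. The stated 30 per arm reproduces. No power figure is given for TSAT.

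**Days between sample and treatment.** Oral iron: 35 − 28 = 7 days off drug at Day 35, or 8 if a 28-day course starting on Day 0 ends on Day 27. FCM: 35 − 7 = 28 days after the second dose. A value carried from Day 28 lies 28 − 7 = 21 days after that dose; one carried from Day 14 lies 7 days after it.

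**Shift in the Day 35 oral-arm mean.** Let f be the share of the oral arm whose Day 35 TSAT is carried from an on-drug visit, and d the post-dose excess in percentage points. Shift = f × d. Neither input is in the documents. I take f = 5, 10, 20% (the 20% echoes the protocol's attrition allowance, which is defined differently) and d = 5, 10, 20.

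| f | d = 5 | d = 10 | d = 20 |
|---|---|---|---|
| 5% | 0.25 | 0.5 | 1.0 |
| 10% | 0.5 | 1.0 | 2.0 |
| 20% | 1.0 | 2.0 | 4.0 |

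The nearest reference is the Phase II mean change of 13.5 points after a single 15 mg/kg dose (Protocol Table 1). The shifts are 0.25/13.5 = 1.9% to 4.0/13.5 = 29.6% of it. The formula gives every carried child the full excess d, so for a given f and d it is an upper bound.

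**Effect on power.** Normal approximation, 36 per arm, oral-arm variance increased by f(1 − f)d², SDs of 6.88 and 11.54 from Table 1, true differences assumed.

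- f = 10%, d = 10, SD 6.88: true 5 points, 86.9% falls to 65.4%; true 10 points, stays near 100%.
- f = 10%, d = 10, SD 11.54: true 10 points, 95.7% falls to 90.2%.
- Worst corner, f = 20%, d = 20, SD 11.54: true 10 points, 95.7% falls to 50.8%.

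These figures move the oral arm alone. If carried FCM values also exceed Day 35 values, by e points in a share g of that arm, the contrast shifts by f × d − g × e against FCM. The sign depends on quantities that the documents do not give.

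**Dropping the treatment-by-visit term.** The treatment effect then averages over Days 7, 14, 28 and 35. With equal visit weights (a simplification) and an average on-drug excess of 5 points across the arm, the pooled oral mean rises by 2/4 × 5 = 2.5 points if Day 28 is off drug, or 3/4 × 5 = 3.75 if it is on drug. LOCF at f = 10% and the same 5 points gives 0.5. Pooling exposes every oral-arm child, whereas LOCF exposes only those without a Day 35 value. With the term kept, an average on-drug excess at earlier visits is absorbed into those visits' treatment means and largely stays out of the Day 35 contrast.

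**The case against.** Much can be said for the plan. An observed scheduled Day 35 TSAT is about a week off oral iron. Protocol 6.3.4 asks for the Day 35 procedures before anyone leaves, which reduces the need for LOCF. By-visit TSAT is descriptive only (SAP 6.2.5). The Day 7 and 14 instructions open with a check made before study drug, and the blood draw follows in the list, so a site might draw before dosing. All this stands as a limit on size. It does not close the gap: the wording does not cover a dose given at home that morning, it is absent at Day 28, and an early-exit sample may itself be on drug.

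A reader might infer that the whole Day 35 TSAT contrast mixes absorption peaks with iron status, or that LOCF favours FCM. The documents support neither. Only missing values and on-drug exit samples are affected. Oral-arm inflation taken alone works against FCM, FCM-arm carry-forward may offset it, and SAP 2.3.4 fills a missing first post-baseline visit with the lowest ITT value, which pulls downward in either arm.

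A reader might also infer that the untimed screening sample biases the comparison or turns away many iron-deficient children. It precedes randomization and affects both arms alike. Mean screening TSAT in Phase II was 7.5% and 3.4%; adding 20 points gives 27.5% and 23.4%, still under the 30% limit, and one re-screen is allowed. Noise in baseline and in some eligibility decisions is what remains.

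**Conclusion.** The point holds in limited form. Oral-arm iron indices at Days 7 and 14 have no fixed relation to the oral dose. Whether Day 28 is on drug cannot be settled from the documents. This adds noise and possible upward error to by-visit TSAT and to any model that pools visits. Separately, a stated LOCF rule puts values from an earlier treatment phase into the Day 35 TSAT and ferritin ANCOVA for participants without a Day 35 value.

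On assumed inputs (5-20% carried forward, 5-20 points excess), the oral-arm TSAT mean moves by 0.25 to 4.0 points. That is negligible at the low end; at the high end it matters if the true difference is modest or the SD large. The net direction across arms is unknown. The screening gap adds noise in both arms without biasing the contrast. Sampling time does not affect the hemoglobin primary analysis. A change is worth making because the better analysis is already written into the SAP.

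**What to change.** 1. **SAP 6.2.1 and 6.2.2.** Make the existing MMRM, with no imputation, the main analysis of Day 35 ferritin and TSAT. Delete the rule that drops a non-significant treatment-by-visit term, and estimate the contrast at Day 35. Without that deletion, the switch could spread the timing problem to the whole oral arm. Keep the LOCF ANCOVA as a sensitivity analysis and add an observed-case Day 35 ANCOVA. State whether an early-exit sample counts as Day 35.
2. **Protocol 6.3.2 and 6.3.3.** Set the order of the Group B blood draw relative to that day's oral dose, as is already done at Day 0. Record the date and time of the last oral iron dose at each draw, including screening. Dose and frequency do not change.
3. **Protocol 5.2 and 3.4.** Reconcile the 28-day course with the Day 28 dosing mark, so that it is clear whether the Day 28 sample is on drug.

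Cost: one eCRF field, minor visit-day logistics, a reordering of analyses already specified and one simple extra ANCOVA. The sample size is unchanged.

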### **6.3.3 Day 28**

- Vitals signs
- Hematology, chemistries and iron indices
- Concomitant medications assessment
- ESA and IBD stability (if applicable)
- Adverse events assessment
- For Group B participants, oral iron compliance assessment

### **6.3.4 Day 35 (End of Study / Early Termination)**

- Physical exam
- Vitals signs
- Hematology, chemistries, and iron indices
- Serum pregnancy test for female participants of child bearing potential
- Concomitant medications assessment
- ESA and IBD stability (if applicable)
- Adverse events assessment
- Log into IRT and enter participant as complete

The participant has completed the study after the Day 35 visit is complete. If for any reason the participant does not complete the study the Day 35 procedures should be completed prior to the participant exiting from the trial.

### **6.3.5 Oral Iron Dose Reduction during the Treatment Phase**

Participants who experience adverse events possibly or probably due to the oral iron during the treatment phase will have their dose of ferrous sulfate reduced from 6 mg/kg to 3 mg/kg while maintaining the same frequency of twice per day. If the participant is receiving tablets, the dose will be reduced from one tablet taken twice daily to one tablet per day.

### **6.3.6 Pharmacokinetic Sampling**

Blood samples will be collected for PK assessment pre-dose, immediately (within 5 minutes) post-dose, and 60 minutes post-dose for participants receiving FCM on Days 0 and 7. Blood samples should be taken at approximately the same time of day (within 1 hour) on Day 7 as Day 0.

The pharmacokinetic parameters to be analyzed in this study are as follows: the maximum serum concentration ( $C_{max}$ ) and the time at which  $C_{max}$  occurs ( $T_{max}$ ), the area under the

serum concentration-time curve from time zero to the last sampling time with a quantifiable concentration ( $AUC_{0-\text{time last measured concentration}}$ ), the extrapolated area under the serum concentration-time curve from time zero to infinity ( $AUC_{0-\text{infinity}}$ ), and the half-life ( $T_{1/2}$ ). The secondary parameters were the mean residence time (MRT), the apparent serum clearance (Cl), and the apparent volume of distribution ( $V_D$ ), which includes the initial volume of distribution following the injection ( $V_{Dc}$ ), the volume of distribution at the steady state ( $V_{Dss}$ ), and the volume of distribution at the final elimination ( $V_{Darea}$ ).

#### 6.4 Central Laboratory Assessments

Serum samples for laboratory analyses must be obtained at all appropriate visits and will be analyzed by the central laboratory. All serum laboratory testing will be provided to the physician for review and assessment. If the Investigator wishes to obtain a follow-up of an abnormal Day 35 laboratory, this laboratory may be obtained after notification of the Sponsor. The laboratory assessments will be determined as listed in Section 3.4.

Hematology:	Hgb, Hct, RBC, WBC, MCV, MCH, MCHC, RDW, platelets, differential count, reticulocyte count, and reticulocyte hemoglobin content (CHr)
Chemistry:	Sodium, potassium, chloride, BUN, creatinine, albumin, alkaline phosphatase, total bilirubin, GGT, AST, ALT, LDH, calcium, phosphorus, glucose, bicarbonate, and magnesium
Iron indices:	Serum iron, serum ferritin, and total iron binding capacity (TIBC), and percentage serum transferrin saturation (TSAT)
Other:	Serum pregnancy test

### 7.0 ASSESSMENT OF SAFETY

#### 7.1 Adverse Events

Any untoward medical event experienced by a participant during the course of this clinical trial, whether or not it is related to the investigational product, at any dose, is considered an adverse event (AE).

For any laboratory abnormality, the investigator will make a judgment as to its clinical significance. If the laboratory value is outside the normal limits and is felt to represent a clinically significant worsening from the baseline value, it should be considered an adverse event and should be recorded on the Adverse Events page of the eCRF. If the laboratory value is outside the normal range, but not an adverse event, the investigator should comment on the findings (i.e., “not clinically significant” or “unchanged from baseline”) in the source documentation [laboratory report]. All laboratory values at the end of study/Day 35 that have been deemed clinical significant by the Investigator should be followed until they are back into normal range.

For the purposes of this study, non-serious anemia (Hgb or Hct below the normal range or worsened from baseline) or iron deficiency (iron indices below the normal range or worsened from baseline) will not be considered adverse events. Anemia or iron deficiency will be considered end points if an intervention is required.

To quantify the severity of adverse events, the National Cancer Institute (NCI)-Common Terminology Criteria for Adverse Events (CTCAE), Version 5 or higher should be used to grade all events. These criteria are provided in the procedure manual.

If a CTCAE criterion does not exist, the investigator should use Table 7.1.1 to assign the adverse event grade.

**Table 7.1.1 Grading of Adverse Event Severity**

Grade	Adjective	Description
1	Mild	Asymptomatic or mild symptoms; clinical or diagnostic observations only; intervention not indicated.
2	Moderate	Moderate; minimal, local or noninvasive intervention indicated; limiting age-appropriate instrumental activities of daily living (i.e., preparing meals, shopping for groceries or clothes, using the telephone, managing money, etc.)
3	Severe	Severe or medically significant but not immediately life-threatening; hospitalization or prolongation of hospitalization indicated; disabling; limiting self-care activities of daily living (i.e., bathing, dressing and undressing, feeding self, using the toilet, taking medications, and not bedridden.)
4	Life-threatening	Life-threatening consequences; urgent intervention indicated.
5	Death	Results in death due to the AE

**Timing:** Non-serious AE will be reported from the initial treatment with \*Study Drug through the completion of the study Day 35. Adverse events will be captured 28 days post the last dose of study drug for participants who receive study drug and terminate early from the trial. This can be completed via a phone call. All ongoing AE's related to study drug (FCM or ferrous sulfate) should be followed until they are no longer related, have taken a confounding medication or return to baseline grade

**Relationship (Causality):** The Investigator will be asked to document his/her opinion of the relationship of the event to the study drug\* as follows:

- NONE            There is *no* evidence of any causal relationship.

- **UNLIKELY** There is *little* evidence to suggest there is a causal relationship. There is *another reasonable explanation* for the event (e.g., the participant's clinical condition, other concomitant treatments).
- **POSSIBLE** There is some evidence to suggest a causal relationship (i.e., there is a reasonable possibility that the adverse experience may have been caused by the agent). However, the influence of other factors may have contributed to the event (e.g., the participant's clinical condition, other concomitant events).
- **PROBABLE** There is evidence to suggest a causal relationship, and the influence of other factors is unlikely.

\* For the purposes of this trial, "study drug" is defined as:

